9.1.6 Follow-up of Adverse Events

All AEs will be followed until stabilization/resolution or until clinical database lock.

All SAEs will undergo active follow-up until resolved or the event becomes chronic or stable. Follow-up data for SAEs obtained after clinical database lock will be incorporated into the safety database.

9.1.7 Reporting Serious Adverse Events to Regulatory Health Authorities/ Institutional Review Boards/Research Ethics Boards/Independent Ethics Committees

The Investigator is responsible for following all local regulations for the reporting of safety information, including the reporting of SAEs to their local IRB/REB/IEC.

The Investigator must promptly report to his or her local IRB/REB/IEC all unanticipated problems involving risks to subjects. This includes death from any cause and all serious adverse events reasonably or possibly associated with the use of study drug.

The Sponsor or their designee is responsible for appropriate reporting of relevant AEs, suspected unexpected serious adverse reactions (SUSARs) involving study drug, to all regulatory authorities.

In addition, the Sponsor or designee will be responsible for the submission of safety letters (e.g., SUSARs) to the central IRB/REB/IEC and to participating Investigators of all SUSARs involving study drug according to applicable regulations.

After termination of the clinical study (determined as last subject, last visit), any unexpected safety issue that changes the risk-benefit analysis and is likely to have an impact on the subjects who have participated in it, will be reported by the Sponsor as soon as possible to the competent authority(ies) concerned together with proposed actions.

9.1.8 Reporting Pregnancies

Pregnancies will be reported from the time the subject signs the informed consent form through final study visit or 30 days after the last study drug administration, whichever is later.

To ensure subject safety, each pregnancy in a subject on study drug must be reported to Pharmacovigilance within 24 hours of learning of its occurrence. Subjects who become pregnant will be withdrawn from the study. The pregnancy should be followed up to determine outcome, including spontaneous or voluntary termination, details of the birth, and the presence or absence of any birth defects, congenital abnormalities, or maternal and/or newborn complications.

Pregnancy should be recorded on a subject's source documents and a Pregnancy Notification and Outcome Form and reported by the Investigator to Pharmacovigilance using the same procedure for reporting SAEs detailed in Section 9.1.5. A pregnancy, by itself, is not an SAE. Pregnancy follow-up should also be recorded and should include an assessment of the possible relationship to the study drug of any pregnancy outcome. Any pregnancy-related SAE (e.g., spontaneous abortion, birth defect) or any other SAE experienced during pregnancy must be recorded on a separate SAE Report Form and reported per SAE reporting procedures in Section 9.1.5.

10 STATISTICS

Part 1 and Part 2. Safety data will be systematically reviewed throughout Part 1 and Part 2 of the study by the independent, unblinded DSMB. Statistical analyses for Part 1 and Part 2 will be described *a priori* in a Statistical Analysis Plan (SAP) generated prior to Part 1 database lock. Any *post-hoc* analyses in either of the Part 1 or Part 2 final reports will be clearly labeled as such. Because both Part 1 and Part 2 will evaluate active treatment and vehicle subjects randomly assigned under a 2:1 active to vehicle schedule, it is anticipated that the Part 1 and Part 2 final reports will present a common set of analyses except for an additional sample size calculation in Part 1. Efficacy and Safety parameters will be statistically evaluated under separate final reports for Part 1 and for Part 2 of the study.

Part 1. Statistical analyses for Part 1 will address both efficacy and safety. Both safety and efficacy data obtained throughout the Part 1 period will be evaluated at the end of Part 1 by the sponsor and/or a contracted statistical organization, both of whom will have remained blinded until Part 1 data lock. The limited sample size of Part 1 may confine certain analyses to the descriptive aspect of the evaluation due to a limited sample size (i.e., inferential p-values may be omitted). Unblinded Part 1 safety and efficacy results will be available to the Sponsor for administrative consideration and use upon completion of Part 1. Efficacy data will be used to generate a sample size estimation for Part 2 as well as to perform between groups and within group descriptive and inferential statistical analyses. Baseline to ending Part 1 change scores for the primary efficacy endpoint (VIIS scaling severity) will be used to calculate a Part 2 samples size under the assumption of a mean change score of .5 units, a standard deviation obtained during Part 1, an alpha of 0.05 and a power of 90%. The sample size will be based on the initial target efficacy area that will have been selected at the beginning of Part 1 and independently evaluated over the 24-week course of the Part 1 study period. Assuming the absence of a safety impairment, the existence of a mean active treatment change score near or greater than 0.5 units, and recruitment feasibility of the estimated sample size, the Sponsor will instigate Part 2 of the trial.

Part 2. Statistical analysis of all Part 2 data will be carried out at the end of Part 2 by the Sponsor and/or a contracted statistical organization, both of whom will have remained blinded until Part 2 data lock. Part 2 analyses will be independent of Part 1 analyses with respect to efficacy parameters and will be used exclusively to support the sponsor's claim. However, at the end of Part 2, all available safety data will be stratified by Part 1 and Part 2 and presented in the Part 2 final report by stratum and overall.

10.1 Sample Size

Part 1 of the study will assess the effect size on the VIIS scaling severity score with ADX-102 1% topical dermal cream, and will confirm the sample size needed for Part 2. Part 2 is expected to require approximately 30 subjects.

The approximate number of 30 subjects for Part 2 was based on the NS-003 Phase 2 study which used the ISS endpoint. The mean ISS Scaling sub-score change from baseline was -0.7 with a standard deviation of 0.52. Conservatively, the change was set to -0.5 and the standard deviation to 0.6. A sample size of 20 achieves 94% power to detect a difference of 0.5 between the null hypothesis mean of 0.0 and the alternative hypothesis mean of -0.5 with an estimated standard deviation of 0.6 and with a significance level (alpha) of 0.05 using a two-sided one-sample t-test. If the above assumptions remain, except that the standard deviation is increased to 0.7, then a sample size of 20 achieves a power of 85%. The sample size of 30 is therefore based on these estimates requiring 20 subjects to be treated with ADX-102 1%. As subjects will be randomized in a 2:1 ratio, 10 subjects will be treated with vehicle.

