- 7. Subject has a history of any malignancy.
- 8. Subject is known to be human immunodeficiency virus positive or had other known immunodeficiency.
- 9. Subject has any clinically significant laboratory test abnormalities or a history of any other condition that, in the opinion of the Investigator, could compromise the subject's ability to comply with the protocol or that could compromise the subject's safety or the interpretation of the study results.
- 10. Subject is currently participating in any other therapeutic clinical study.
- 11. Subject is pregnant or lactating.

Statistical Analysis:

Part 1 and Part 2 will be analyzed in a similar fashion with the exception that the Part 1 analysis will include a sample size evaluation. Part 1 analyses in some instances may be confined to the descriptive aspect of the evaluation (i.e., inferential p-values may be omitted) due to the small sample size of 6 treated and 3 control patients.

The primary efficacy endpoint (VIIS scaling severity as assessed by the Investigator in the target efficacy area) as well as all secondary efficacy variables that are captured on a continuous or semi-continuous

scale

will be expressed as baseline to ending change scores. Two-sided 95% confidence intervals (CIs) will be computed and used descriptively for all variables but also to evaluate change relative to a standard for some variables (i.e., by determining whether the CI includes or excludes the standard).

The two-sided 95% CI for VIIS scaling severity will be used to evaluate the primary endpoint as follows. An efficacy claim from Part 2 will be made if: 1) the lower confidence interval is above zero, 2) the midpoint of the confidence interval is at least 0.5 units is size, and 3) at least 50% of subjects have favorable change scores of one or greater.

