Response over time will be converted to one or more Area Under the Curve parameters and evaluated using a generalized linear model. VIIS outcome scores and other continuous or semi-continuous outcome variables will be evaluated using a Mixed Model Repeated Measures (MMRM) analysis. Conversion of VIIS or other scales to indicate response (yes/no) will occur (e.g., 0.5 VIIS improvement, 1 unit VIIS improvement) and be evaluated as secondary endpoints. Logistic or Generalized Estimating Equation (GEE) modeling will be used to evaluate incidence of response overall and/or by time. Time to Event analysis (e.g., Kaplan-Meier with log rank test, proportional hazards [PH] modeling) will be used to evaluate time to response.

To increase statistical power, covariates may be incorporated into the computation of 95% confidence intervals (e.g., through the use of a mean centered covariate in a regression model to predict the mean pre-treatment to post-treatment difference) and/or into logistic, GEE, PH, MMRM and generalized linear models.

All analyses will be specified *a priori* in an Statistical Analysis Plan (SAP) to be completed prior to database lock for Part 1. The SAP will serve as the summative and definitive plan of analysis. Analyses not described in the SAP will be labeled as *post-hoc*. The SAP will outline all analyses that will be performed in Part 1 and in Part 2 of this study.

Sample Size Rationale:

Part 1 will assess the effect size on the VIIS scaling severity score, and will confirm the sample size needed for Part 2. Part 2 is expected to require approximately 30 subjects.

Data Safety Monitoring Board:

An independent data safety monitoring board (DSMB) will be established to review all available safety data after approximately 9 subjects have completed Week 24 in Part 1. The assessment of safety will be determined from dermatological endpoints, vital sign measurements, physical examinations, hematology and chemistry laboratory testing, ECG readings, use of concomitant medications, and review of AEs. Based on the safety data provided, the DSMB will provide recommendations about stopping or continuing the trial.

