10.4 Efficacy Analyses

A conclusion concerning efficacy will be based on evaluation of data in Part 2. A primary efficacy analysis will be conducted as well as a number of secondary efficacy analyses.

The primary efficacy endpoint (VIIS scaling severity as assessed by the Investigator in the target efficacy area) as well as all secondary efficacy variables that are captured on a continuous or semi-continuous scale (e.g., VIIS erythema score, central reader assessed VIIS scales, EQ-5D-5L, clinical global impression of severity, Patient/Observer impression scales, Patient-Reported Itching, CDLQI/DLQI, lipid biomarkers and TEWL) will be expressed as baseline to ending change scores. Two-sided 95% confidence intervals (CIs) will be computed and used descriptively for all variables but also to evaluate change relative to a standard for some variables (i.e., by determining whether the CI includes or excludes the standard).

The two-sided 95% CI for VIIS scaling severity will serve as the primary analysis and will be used to evaluate this primary endpoint as follows. An efficacy claim will be made if: 1) the lower confidence interval is above zero, 2) the mid-point of the confidence interval is at least 0.5 units is size, and 3) at least 50% of subjects have favorable change scores of one or greater.

The primary and secondary scores measured on a continuous or semi-continuous scale also will be evaluated using Mixed Model Repeated Measures to assess the effects of treatment (active vs. vehicle), time (per collection schedule), and treatment x time. In addition to descriptive statistics for the raw data used in each model, the LS means and standard errors will be reported for each main effect and interaction, as well as for treatment contrasts (i.e., active LS mean minus vehicle LS mean) at each data collection time point. If informative, covariates may be added to one or more models. Statistical significance unadjusted for multiplicity for main effects, interactions and contrasts will be reported. However, neither the main effect of treatment nor the treatment contrasts at time points are expected to be statistically significant ($p \le 0.05$) due to power restrictions at the between group level imposed by recruiting realities.

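### The 94%, 85% and 90% power figures for Part 2 cover only the first of three claim conditions; if the true mean change is 0.5, the full rule is met in at most about 60% of trials

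*Protocol*

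**What the plan says.** Protocol section 10.1 starts from NS-003: "The mean ISS Scaling sub-score change from baseline was -0.7 with a standard deviation of 0.52". It then discounts: "Conservatively, the change was set to -0.5 and the standard deviation to 0.6". With a two-sided one-sample t-test at alpha 0.05 it states "A sample size of 20 achieves 94% power to detect a difference of 0.5", falling to 85% if the SD is 0.7. That gives 20 ADX-102 subjects and, at 2:1, 10 on vehicle.

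The Part 1 paragraph of section 10 says the Part 2 size will be recalculated assuming "a mean change score of .5 units, a standard deviation obtained during Part 1, an alpha of 0.05 and a power of 90" percent.

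Section 10.4 sets the Part 2 claim rule. Condition 1 is a lower 95% confidence limit above zero. The other two are "the mid-point of the confidence interval is at least 0.5 units is size, and 3) at least 50% of subjects have favorable change scores" of at least one. The synopsis repeats the rule ("the midpoint of the confidence interval is at least 0.5 units is size"). Section 10 makes Part 2 the only basis for the efficacy claim.

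No section gives the probability of meeting all three conditions. SAP section 2 limits the SAP to Part 1, so its success criterion in section 10.1 does not replace the Part 2 rule.

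**The concern.** The trial is sized on one event and judged on another. The t-test in section 10.1 is the same event as condition 1. Conditions 2 and 3 are additional hurdles, and the planning effect of 0.5 is exactly the value that condition 2 requires the observed mean to reach. An estimate reaches its own true value only about half the time, and a larger sample does not change that.

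A sponsor, DSMB or ethics committee could take 94%, 85% or 90% as the chance that Part 2 supports a claim at a mean change of 0.5. It is not. Section 10 also starts Part 2 when the Part 1 active mean is close to 0.5 or above, which includes the region where the rule is near a coin toss. The disease is very rare, so the true chance of a claim should be known before the second set of subjects is enrolled.

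**Working it through.** Improvement is counted as positive throughout.

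**1. The plan's own figures.** For a one-sample t-test the noncentrality is √n × mean / SD.
- SD 0.6: √20 × 0.5/0.6 = 3.727; critical t (19 df) 2.093; power 94.2% (plan: 94%).
- SD 0.7: √20 × 0.5/0.7 = 3.194; power 85.8% (plan: 85%).
- Resizing rule (mean 0.5, 90%): SD 0.52 gives n = 14 (91.3%), SD 0.6 gives n = 18 (91.5%), SD 0.7 gives n = 23 (90.5%).

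Section 10 does not name the test behind its 90%. Its inputs (a mean, an SD, alpha) can describe condition 1 but not a responder condition.

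**2. Condition 2 at a true mean of 0.5.** The midpoint of the interval is the sample mean. In the simplest case each subject changes by 0 or 1 with probability ½. With n = 20, P(at least 10 improve) = 0.5 + 0.5 × P(exactly 10) = 0.5 + 0.5 × 0.176 = 58.8%. Condition 3 is then the same event, and condition 1 holds in 99.9% of trials, so the full rule is met in 58.8%. With n = 23 there is no tie and it is met in 50.0%.

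**3. Full rule at the plan's SDs.** Assumptions not in the documents: changes of −1, 0, 1 or 2 grades (SAP section 10.1 describes VIIS as a five-point scale, 0–4), the rule applied to the ADX-102 arm, and no dropout. Let a and d be the probabilities of −1 and +2.
- Matching mean and SD fixes a + d = (SD² + mean² − mean)/2. At mean 0.5 this is (0.36 + 0.25 − 0.50)/2 = 0.055 for SD 0.6, and (0.49 + 0.25 − 0.50)/2 = 0.12 for SD 0.7.
- The responder rate is mean + a − d, so it can run from 0.445 to 0.555 (SD 0.6) or 0.38 to 0.62 (SD 0.7).

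The probability of meeting all three conditions is summed exactly over the multinomial outcomes across that whole range:

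| True mean | SD | n | t-test power | All three conditions |
|---|---|---|---|---|
| 0.5 | 0.6 | 20 | 94.2% | 39–58% |
| 0.5 | 0.7 | 20 | 85.8% | 19–58% |
| 0.5 | 0.52 | 14 | 91.3% | 57–60% |
| 0.5 | 0.6 | 18 | 91.5% | 41–59% |
| 0.5 | 0.7 | 23 | 90.5% | 12–51% |
| 0.5 | 0.6 | 100 | near 100% | 16–54% |
| 0.7 | 0.52 | 20 | 99.99% | 96–97% |

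Odd n is lower because of the 50% condition: at mean 0.5 and SD 0.6, n = 19 gives 31–51% and n = 21 gives 30–51%. Allowing changes from −2 to +3 raises the maximum only to 59% at n = 20, 60% at n = 18 and 61% at n = 14. At n = 20, dropping condition 1 altogether still leaves a ceiling of 58%.

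**4. Resized trials if the true mean is 0.7.** SD 0.52, n = 14: 94.5–94.8%. SD 0.6, n = 18: 91–94%. SD 0.7, n = 23: 72–91%.

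**5. Sensitivity to what the protocol leaves open.**
- Part 2 has two Investigators score VIIS at baseline (section 6.9; Table 2, footnote 6) with no combining rule, and averaging would create half grades. As an illustration, simulated normal scores rounded to half grades (n = 20) meet the rule in about 45% of trials at 0.7/0.52 and 10% at 0.5/0.6.
- Section 10.4 says only subjects, not which arm. If condition 3 counts all 30 and the vehicle responder rate is 0–40% (assumed), the rule is met in 31–93% at 0.7/0.52 and 1–48% at 0.5/0.6.

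**6. False claims.** At a true mean of 0 and n = 20 the full rule is met in at most 0.02% (SD 0.6) or 0.11% (SD 0.7) of trials.

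**The case against.** **Nothing printed is miscalculated.** This stands. Section 10.1 names its test, null and alternative, and never calls 94% the chance of a claim. A reader might infer that the power figures are wrong; they reproduce. What is missing is the probability for the rule that decides the claim.

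**A figure near 50% is built into any rule that asks the estimate to reach the assumed truth.** This is also true. Powering a significance test at a discounted effect and adding relevance thresholds is a legitimate choice, and 0.7, not 0.5, is the NS-003 result. That limits the finding to a true mean at or near 0.5. But 0.7 is uncertain for this purpose: NS-003 used ISS rather than VIIS, for 8 weeks on about 3% BSA, in 12 subjects randomized 1:1. If 0.7 and 0.52 come from six treated subjects, the 95% CI is 0.7 ± 2.571 × 0.52/√6, about 0.15 to 1.25.

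**The protocol admits limited power.** Only for the active-versus-vehicle comparison: section 10.4 refers to "power restrictions at the between group level imposed by recruiting realities". The claim rule is not that comparison.

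**Covariates may tighten the interval.** The synopsis and section 10.4 mention, as an example, "the use of a mean centered covariate in a regression model to predict the mean pre-treatment to post-treatment difference". In a least-squares fit with centring within the analysed arm, the midpoint stays at the sample mean, so only condition 1 gains. It would be too strong to say that no covariate adjustment matters: centring on a pooled two-arm mean would move the midpoint.

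**A Part 2 SAP may deal with this.** Possibly. The protocol promises SAP coverage of both parts, but the SAP supplied covers Part 1 only. The sizing statement and the claim rule both stand in the protocol, which is where they need to agree.

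**Conclusion.** The concern holds as a gap between the sizing calculation and the claim rule. The 94%, 85% and 90% describe condition 1 only. If the true mean change is 0.5, all three conditions are met in at most about 60% of trials at any size the resizing rule would plausibly return (n = 14 upward). The section 10 rule therefore cannot give 90% for the claim at that effect. This rests on whole-grade changes and on applying the rule to the ADX-102 arm.

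Three stronger readings are not supported. First, a reader might infer that resizing can never reach 90% for the claim; at a true mean of 0.7 it can, as step 4 shows. Second, a reader might infer that Part 2 is bound to be too small; at the NS-003 values 20 treated subjects meet the rule in about 97% of trials. That figure needs the same assumptions and the transfer from ISS to VIIS, and half-grade scores or counting all 30 subjects could lower it greatly. Third, the false-claim rate is not raised; the extra conditions make it very small.

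**What to change.** 1. In sections 10.1 and 10, label 94%, 85% and 90% as power for condition 1 of section 10.4 only.
2. In section 10.1, have the sponsor compute and state the probability of meeting all three conditions at 0.5 and at the NS-003 values. State the score distribution, responder rate, arm and handling of the two baseline ratings. The figures above show the size of the gap and should not be copied into the protocol.
3. If 90% is wanted for the claim, base the section 10 calculation on the joint rule at a stated alternative above 0.5. Check odd and even n, because the 50% condition makes the probability saw-toothed.
4. In section 10.4, name the subjects to whom the conditions apply. Use one sign convention: section 10.1 writes improvement as −0.5, while condition 1 needs a limit above zero.

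The cost is protocol wording and a short calculation. The stated chance of success at 0.5 becomes less favourable. Relabelling and disclosure need no extra patients; sizing on the joint rule might, depending on the alternative and responder rate chosen.

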10.2 Analysis Populations

The statistical analysis will be based on the analysis populations as defined below

Safety Population	All randomized subjects who use at least one dose of study drug, regardless of whether they undergo any study assessments.
Intent-to-Treat (ITT) Population	All randomized subjects who use at least one dose of study drug and have any post-dose assessments. Subjects are evaluated according to the study drug to which they are randomized.
Per-Protocol (PP) Population	All ITT subjects will be considered PP if they dose with study drug and do not deviate from the protocol.

The following is a list of protocol violations which would exclude subjects from the PP population:

- Subject did not receive study drug as assigned.
- Subject did not meet all inclusion/exclusion criteria.

10.3 Accountability and Background Characteristics

10.3.1 Enrollment and Disposition

The number of subjects enrolled, by study population and Investigative site, will be presented by treatment group. The primary reasons for discontinuation will be summarized by treatment and based on the safety population. The number and percentage of subjects with protocol deviations or subjects requiring rescue therapy leading to exclusion from the PP population will be presented by reason for exclusion, stratified by treatment. All deviations and rescued subjects will be listed.

